5.1.4.1 Adequate Non-Hormonal Contraception

Adequate contraception is defined as one highly effective form (i.e. abstinence, (fe)male sterilization) OR two effective forms (e.g. non-hormonal IUD and condom / occlusive cap with spermicidal foam / gel / film / cream / suppository).

5.1.4.2 Timing and Duration of Contraception

- Females

Palbociclib can cause fetal harm when administered to a pregnant woman. Females of reproductive potential will be advised to use effective contraception during treatment with Palbociclib and for at least 3 weeks after the last dose.

- Males

Because of the potential for genotoxicity, male patients with female partners of reproductive potential will be advised to use effective contraception during treatment with Palbociclib and for 3 months after the last dose.

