	
Inclusion Criteria specific for patients enrolled on Group A
 
I.11 Patients must be able and willing to swallow and retain oral medication
 
I.12 Absolute neutrophil count (ANC) $\geq 1,500/\text{mm}^3$
 
I.13 Platelets $\geq 120,000/\text{mm}^3$
 
I.14 Hemoglobin $\geq 10\text{g/dL}$
 
I.15 Total serum bilirubin $\leq \text{ULN}$; or total bilirubin $\leq 3.0 \times \text{ULN}$ with direct bilirubin within normal range in patients with documented Gilbert's Syndrome.
 
I.16 Aspartate amino transferase (AST or SGOT) and alanine amino transferase (ALT or SGPT) $\leq 1.5 \times$ institutional ULN
 
I.17 Serum creatinine within normal institutional limits or creatinine clearance $\geq 50 \text{ mL/min}/1.73 \text{ m}^2$ for patients with serum creatinine levels above institutional ULN.
 
I.18 Pregnancy must be ruled out:
 
 a) Serum or urine pregnancy test must be negative within 14 days of treatment start in women of childbearing potential. b) Pregnancy testing does not need to be pursued in patients who are judged as postmenopausal before enrollment, or who have undergone tubal ligation, bilateral oophorectomy, total hysterectomy 
I.19 Willingness to undergo adequate contraception if childbearing potential
 
 a) Women of childbearing potential and male patients randomized into treatment Group A must use adequate contraception for the duration of protocol treatment and for 3 months after the last treatment with palbociclib if they are in Group A. b) Adequate contraception is defined as one highly effective form (i.e. abstinence, (fe)male sterilization) OR two effective forms (e.g. non-hormonal IUD and condom / occlusive cap with spermicidal foam / gel / film / cream / suppository). 
There are no Inclusion Criteria specific for patients enrolled on Group B

--	---

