3.2 End of Treatment

The total duration of Palbociclib treatment is 12 days, beginning any time after enrollment. Definitive surgery will occur 3 (+/- 1day) after end of palbociclib treatment, on study day #15 +/- 1 day. The end of treatment visit will occur 32 (+/- 8 days) after surgery. Unless a patient discontinues treatment early or experiences treatment delays, this would result in 24-40 days on trial. Any premature, permanent termination of IP treatment is referred to as "Early End of IP-treatment". "End of IP treatment per protocol" means Palbociclib treatment ended after 12 days.

Any one of the following criteria will be reason to stop IP-treatment before 12 days:

- General or specific changes in the participant's condition render the participant not a candidate for further treatment in the opinion of the treating investigator
- Unacceptable toxicity or unacceptable adherence to palbociclib.
- Patient withdraws consent

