I.15	Total serum bilirubin $\leq \text{ULN}$; or total bilirubin $\leq 3.0 \times \text{ULN}$ with direct bilirubin within normal range in patients with documented Gilbert's Syndrome.
I.16	Aspartate amino transferase (AST or SGOT) and alanine amino transferase (ALT or SGPT)

	$\leq 1.5 \times$ institutional ULN
I.17	Serum creatinine within normal institutional limits or creatinine clearance ≥ 50 mL/min/1.73 m ² for patients with serum creatinine levels above institutional ULN.
I.18	
Pregnancy must be ruled out:
 
Serum or urine pregnancy test must be negative within 14 days of treatment start in women of childbearing potential.
 
Pregnancy testing does not need to be pursued in patients who are judged as postmenopausal before enrollment, or who have undergone tubal ligation, bilateral oophorectomy, total hysterectomy

I.19	
Willingness to undergo adequate contraception if childbearing potential
 
Women of childbearing potential and male patients randomized into treatment Group A must use adequate contraception for the duration of protocol treatment and for 3 months after the last treatment with palbociclib if they are in Group A.
 
Adequate contraception is defined as one highly effective form (i.e. abstinence, (fe)male sterilization) OR two effective forms (e.g. non-hormonal IUD and condom / occlusive cap with spermicidal foam / gel / film / cream / suppository).

There will be no specific criteria for Group B since this is a biorepository only group.

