4.5.5 Surgery

On the scheduled day for surgery patient will follow surgery team's recommendations for hospital registration, OR procedures and subsequent discharge home. Surgery will occur on study day 15 +/-1. Research tumor sample will be collected under the supervision of certified pathologist (Tumor Sample #2). The research tumor sample will be transported to [name] Lab where it will be processed and stored for testing. The surgery must happen at the study participating center.

4.5.6 Follow up phases – End of Study Visit and Long Term Follow Up

Follow-Up Phase starts on post operative day #1. The End of Study Visit (EOV) occurs on treatment day 32 +/- 8, which represents a time point situated approximately at 2 to 3 weeks after surgery. On that date, there will be a clinic visit with physical examination/vital signs, ECOG performance status assessment, adverse events, serious adverse events, current medications, and final pathology report. Additional treatments may be required after definitive surgery. Patient will discuss any additional treatments with the primary or treating medical oncologist. Laboratory tests will include CBC, CMP and an additional blood sample for research. A Long Term Follow up (LTF) assessment may be done at year 1 (+/- 30 days) and at year 5 (+/- 60 days) from treatment. The LTF assessment may comprise of Electronic Medical Record Review for clinical data and survival status as well as of a telephone call.

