5.1.4 Pregnancy and Contraception Use

Pregnancy is contraindicated during Palbociclib therapy and for at least 3 weeks after the last dose. Based on findings from animal studies and its mechanism of action, Palbociclib can cause fetal harm when administered to a pregnant woman. There are no available data in pregnant women to inform the drug-associated risk. In animal reproduction studies, administration of palbociclib to pregnant rats and rabbits during organogenesis resulted in embryofetal toxicity at maternal exposures that were ≥ 4 times the human clinical exposure based on AUC. Patients will be advised regarding the potential risk of Palbociclib exposure to a fetus. The estimated background risk of major birth defects and miscarriage for the indicated population is unknown. In the U.S. general population, the estimated background risk of major birth defects and miscarriage in clinically recognized pregnancies is 2–4% and 15–20%, respectively.

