5.1.5 Lactation

There is no information regarding the presence of palbociclib in human milk, nor its effects on milk production or the breastfed infant. Because of the potential for serious adverse reactions in breastfed infants from Palbociclib, advise a lactating woman not to breastfeed during treatment with Palbociclib and for 3 weeks after the last dose.

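### Women in Group A are given two contraception periods after the last palbociclib dose: 3 months in I.19, at least 3 weeks in section 5.1.4.2

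*Combined protocol and SAP*

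**What the plan says.** I.19 appears with the same duration in three places. In section 4.1.1 it states that women of childbearing potential and male patients in Group A "must use adequate contraception for the duration of protocol treatment and for 3 months after the last treatment with palbociclib". The synopsis and the eligibility checklist in Appendix E repeat the period: "for 3 months after the last treatment with palbociclib if they are in Group A".

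The safety section gives women a different period. Section 5.1.4.2 says that females of reproductive potential "will be advised to use effective contraception during treatment with Palbociclib and for at least 3 weeks after the last dose". For men with female partners of reproductive potential, the same section requires contraception "during treatment with Palbociclib and for 3 months after the last dose".

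Two neighbouring sections also use 3 weeks. Section 5.1.4 states: "Pregnancy is contraindicated during Palbociclib therapy and for at least 3 weeks after the last dose". Section 5.1.5, on lactation, says to "advise a lactating woman not to breastfeed during treatment with Palbociclib and for 3 weeks after the last dose".

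**The concern.** Two operative rules give different minimum periods for the same precaution in the same women. The protocol says that palbociclib can harm a fetus, so the period is a safety instruction. Staff who counsel from section 5.1.4.2, the natural place to look, can correctly tell a woman that 3 weeks is enough. If she then stops, she has followed section 5.1.4.2 and broken I.19.

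Sites also could not classify that event consistently. Section 8.8 requires the study to be run exactly as the approved protocol describes, and a woman who stops in week 5 after her last dose complies with one section and deviates from another.

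The documents do not settle which period is intended. I.19 carries 3 months wherever it is printed, while sections 5.1.4, 5.1.4.2 and 5.1.5 all carry 3 weeks.

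**Working it through.** The plan gives no figure of its own to reproduce. The check sets the texts side by side and does the calendar arithmetic.

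**The texts compared**

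| Place | Women | Men | Force |
|---|---|---|---|
| I.19 (synopsis, 4.1.1, Appendix E) | 3 months | 3 months | mandatory |
| 5.1.4.2 | at least 3 weeks | 3 months | advice |
| 5.1.4 (pregnancy contraindicated) | at least 3 weeks | – | contraindication |

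Only the female durations differ. The male durations agree, although I.19 covers all male patients in Group A and section 5.1.4.2 only those with female partners of reproductive potential.

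**Inputs**

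- Last dose: Day 12 (section 3.1.1).
- 3 weeks = 21 days.
- 3 calendar months = 89 to 92 days, depending on the date of the last dose (checked for every date from 2018 to 2025).
- Surgery: Day 15 +/- 1, that is Day 14 to 16 (section 3.1.1).
- Final clinic visit: section 4.5.6 says "The End of Study Visit (EOV) occurs on treatment day 32 +/- 8", and Appendix A agrees. Section 3.2 says "The end of treatment visit will occur 32 (+/- 8 days) after surgery". Both readings are carried below.

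**Size of the difference**

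- End of the 3-week period: 12 + 21 = Day 33.
- End of the 3-month period: 12 + 89 = Day 101, to 12 + 92 = Day 104.
- Difference: 89 − 21 = 68 days, to 92 − 21 = 71 days.

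**How much of the I.19 period is left after the final clinic visit**

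- Visit on Day 32 +/- 8 (Day 24 to 40): 101 − 40 = 61 days, to 104 − 24 = 80 days.
- Visit 32 +/- 8 days after surgery: earliest 14 + 24 = Day 38, latest 16 + 40 = Day 56. Remaining: 101 − 56 = 45 days, to 104 − 38 = 66 days.

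The next contact is the optional long-term follow-up at year 1 +/- 30 days. Its earliest date is about 365 − 30 = 335 days from treatment, well after Day 104. On either reading, no study contact is scheduled between the final clinic visit and the end of the I.19 period.

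**The case against.** The strongest reply is that the two texts can be followed together. In section 5.1.4.2, 3 weeks is a floor and is worded as advice, whereas I.19 is an obligation. A woman who observes I.19 satisfies every section, so the binding rule can be identified. Section 5 could be read as a drug-level minimum and I.19 as a stricter study rule. I.19 is also on the checklist that the investigator signs before registration, so each woman concerned is screened against the 3-month text before dosing. The final clinic visit falls inside the 3-month period and could be used to repeat or correct the advice.

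Much of this stands. The floor makes the conflict one-directional, the checklist lowers the chance that a woman hears only the shorter period, and the final visit is an opportunity. It does not remove the conflict. No text says that I.19 overrides section 5.1.4.2. The procedures listed for the final visit in section 4.5.6 do not include contraception advice. Under the reading in section 3.2, the visit always comes after Day 33, when the 3-week period is already over.

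Two further points are fair. The three printings of I.19 are one rule copied, not three independent statements of intent. The lactation text is about breastfeeding and bears only on which period the authors had in mind for women. Likewise, section 5.1.4 is a pregnancy contraindication with a floor of its own, so it does not strictly contradict I.19. Changing it is for consistency.

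**Conclusion.** The inconsistency is real and the text is wrong as written. For women of childbearing potential in Group A, the two stated minimum periods differ by 68 to 71 days, and counselling that follows section 5.1.4.2 to the letter permits a breach of I.19.

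The point is minor. It concerns only the women of childbearing potential among the 12 Group A patients, a number the documents do not give and which could be zero. No endpoint or analysis is touched, and the documents give no evidence that fetal risk is raised between 3 weeks and 3 months.

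The day numbers assume a last dose on Day 12. If dosing stops early, both end dates move together and the 68 to 71 day difference is unchanged. The consent form was not available for review, so what women are told in writing is unknown.

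**What to change.** State one post-treatment contraception period for women and use it everywhere.

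- **Default, unless the sponsor confirms that 3 weeks is intended for women:** change the female sentence in section 5.1.4.2 to 3 months, and bring the opening sentence of section 5.1.4 into line. This keeps the wording that is already mandatory and on the signed checklist.
- **If 3 weeks is intended for women:** split I.19 by sex in the synopsis, section 4.1.1 and Appendix E, with at least 3 weeks for women and 3 months for men.

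Check that the consent form carries the same period. The protocol cost is one sentence in each of two sections, or one criterion in three places. No visit or test is added.

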5.1.5 Lactation

There is no information regarding the presence of palbociclib in human milk, nor its effects on milk production or the breastfed infant. Because of the potential for serious adverse reactions in breastfed infants from Palbociclib, advise a lactating woman not to breastfeed during treatment with Palbociclib and for 3 weeks after the last dose.

5.1.6 Geriatric Use

Geriatric participation is allowed in this study. Of 84 patients who received Palbociclib in a study, 37 patients (44%) were ≥ 65 years of age and 8 patients (10%) were ≥ 75 years of age. Of 347 patients who

received Palbociclib in Study 2, 86 patients (25%) were ≥ 65 years of age. No overall differences in safety or effectiveness of Palbociclib were observed between these patients and younger patients.

5.2 Safety Parameters and Definitions

5.2.1 Adverse Events

According to the ICH guideline for Good Clinical Practice, an adverse event is any untoward medical occurrence in a clinical investigation subject administered a pharmaceutical product, regardless of causal attribution. An adverse event can therefore be any of the following:

- a. Any unfavorable and unintended sign (including an abnormal laboratory finding), symptom, or disease temporally associated with the use of a medicinal product, whether or not considered related to the medicinal product
- b. Any new disease or exacerbation of an existing disease (a worsening in the character, frequency, or severity of a known condition).
- c. Recurrence of an intermittent medical condition (e.g., headache) not present at baseline
- d. Any deterioration in a laboratory value or other clinical test (e.g., ECG, X-ray) that is associated with symptoms requires additional diagnostic testing or medical/surgical intervention, leads to a change in study treatment or concomitant treatment or discontinuation from study drug or is considered to be an AE by the Investigator.
- e. Adverse events that are related to a protocol-mandated intervention, including those that occur prior to assignment of study treatment.

The investigator is responsible for ensuring that all adverse events (as defined above) are recorded on the respective Adverse Event eCRF page and additionally reported to the IRB in case the AE fulfills the criteria for expedited reporting.

For each adverse event recorded on an Adverse Event eCRF page, the investigator will make an assessment of seriousness, severity, and causality. The prompt reporting of adverse events is the responsibility of each investigator engaged in clinical research, as required by applicable regulations. Adverse events must be described and graded using the terminology and grading categories as defined by NCI's Common Terminology Criteria for Adverse Events (CTCAE), Version 4.0.

As part of ongoing safety reviews conducted by the Sponsor, any non-serious adverse event that is determined by the Sponsor to be serious will be reported by the Sponsor as an SAE. To assist in the determination of case seriousness further information may be requested from the investigator to provide clarity and understanding of the event in the context of the clinical study.

5.2.2 Serious Adverse Events (Immediately Reportable to the Sponsor)

For this protocol, serious adverse events (SAEs) are defined as follows:

- It results in death (i.e., the AE actually causes or leads to death).
- It is life threatening (i.e., the AE, in the view of the investigator, places the subject at immediate risk of death. It does not include an AE that, had it occurred in a more severe form, might have caused death.).
- It requires or prolongs inpatient hospitalization.
- It results in persistent or significant disability/incapacity (i.e., the AE results in substantial disruption of the subject's ability to conduct normal life functions).
- It results in a congenital anomaly/birth defect in a neonate/infant born to a mother exposed to Palbociclib.
- It is considered a significant medical event by the investigator based on medical judgment (e.g., may jeopardize the subject or may require medical/surgical intervention to prevent one of the outcomes listed above).

5.2.3 Non-Serious Adverse Events of Special Interest (Immediately Reportable to the Sponsor)

This study will not have adverse events of special interest (AESI) for reporting.

There are no protocol-specified SAEs in this study.

5.2.4 Medication errors

Medication errors may result from the administration or consumption of the wrong drug, by the wrong patient, at the wrong time, or at the wrong dosage strength. Such medication errors occurring to a study participant are to be captured on the medication error CRF which is a specific version of the adverse event (AE) page, and on the SAE form when appropriate. In the event of medication dosing error, the Sponsor PI should be notified immediately (within 24hr from learning about the event).

Medication errors are reportable irrespective of the presence of an associated AE/SAE, including:

- Medication errors involving patient exposure to the investigational product
- Potential medication errors or uses outside of what is foreseen in the protocol that do or do not involve the participating patient.

Whether or not the medication error is accompanied by an AE, as determined by the investigator, the medication error should be captured on the medication error version of the adverse event (AE) page and, if applicable, any associated adverse event(s) are captured on an adverse event (AE) CRF page.

5.3 Methods and Timing for Capturing and Assessing Safety Parameters

5.3.1 Adverse Event Reporting Period

Adverse event (Safety) reporting is mandatory from the date of informed consent form signature (i.e., screening phase) until the last visit of the treatment phase, 26 to 32 days after surgery. During the Screening Phase, only AEs deemed to be serious (SAEs) and related to protocol mandated and to non-routinely performed procedures have to be reported.

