Collection of tissue at definitive surgery (sample #2): A certified pathologist will be responsible for tissue handling and destination to research. Unfortunately, performing a research-only core at surgery is not felt to be practical in patients with diagnosis of DCIS, since one of the key components of pathologic exam is to rule out invasive component. Therefore, an additional core at surgery is not felt to be safe for patients. Tissue will be collected for translational studies based on certified pathologist examination of material and without compromise of definitive diagnosis. There is a possibility that at definitive surgery invasive lesions are detected. We will describe the same parameters for DCIS lesions and for invasive lesions. Invasive component histologic abnormalities description will be purely exploratory. The focus of this study is DCIS. Pathologist will fill out a form confirming collection of sample for the trial ([Appendix L](#))

Follow up period: Patients will be followed at the postoperative period in the outpatient setting, at which point any additional systemic treatment for DCIS or invasive breast cancer will be discussed. The End of Study visit will occur approximately 2 to 3 weeks after surgery. The Informed Consent form will contain terminology asking patients for permission for the researchers to review the medical chart at 1 year and at 5 years from enrollment to collect additional clinical information about medical history, disease status and treatments.

The study procedures are summarized in [Appendix A](#).

The study schema is presented in [Appendix B](#).

The calendar template for treatment and visits timeline planning based on surgery date for patients enrolled on treatment Group A (Palbociclib) is presented in [Appendix C](#).

The Enrollment Process to Treatment Overview is presented in [Appendix D](#).

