4.5 Study Assessments

The study consists of 6 different phases:

1) Pre-Screening Phase	(candidates for study either on Group A or Group B)	
2) Screening Phase	(Group A and Group B)	Study Days -28 to 0
3) Treatment Phase	(Group A only)*	Study Days 1 to 12
4) Pre-Surgery Phase	(Group A only)*	Study Days 12 to 14
5) Surgery	(Group A and Group B)*	Study Days 14 to 16
6) Follow-Up Phase - EOF	(Group A and Group B)	Study Days 25 to 40
Follow-Up Phase - LTF	(Group A and Group B)	EMR review 1yr and 5yr

* Please refer to item **3.1.1 Overview of Study Design, timing of surgery**, for additional details on definitive surgery timing after enrollment for patients on Group B

See **Appendix A Study Procedures** and **Appendix B Study Schema** for details as to how these phases correspond with the Schedule of Assessments calendar, Pre-Screening Phase, Screening Phase, Treatment Phase, Pre-Surgery Phase, Surgery and Follow-Up Phases End of Study Visit (EOF) and Long Term Follow Up (LTF).

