4.5.4 Pre-Surgery phase

For patients enrolled to **Group A**, on Day 13 +/-1 there will be a pre-operative clinic visit, when tolerance to therapy will be assessed, including physical examination/vital signs, ECOG performance status assessment, adverse events, serious adverse events, IP accountability, concomitant medications, measurements of treatment adherence. Laboratory tests will include CBC, CMP and an additional blood sample for research (please refer to item **4.5.2.7 Mandatory Blood Samples for Biomarker Analysis**). After this visit, patients will proceed to scheduled definitive surgery for DCIS. Treatment phase ends on the day of surgery (Day 15 +/-1).

For patients enrolled to **Group B** the pre-surgery experimental phase will only involve Laboratory tests including CBC, CMP and an additional blood sample for research (please refer to item **4.5.2.7 Mandatory Blood Samples for Biomarker Analysis**).

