5.4.2.4 SAE Reporting Period

The SAEs that are subject to this reporting provision are those that occur from after the first dose of Palbociclib through 28 calendar days after the last administration of the Pfizer Product. In addition, if Principal Investigator becomes aware of an SAE occurring any time after the administration of the last dose of the Palbociclib, Sponsor PI should report that SAE to Pfizer if a causal relationship between the Pfizer Product and the SAE is suspected.

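### Section 5.3.1 ends adverse-event reporting on days that the scheduled post-surgery visit almost never reaches, and no contact is fixed at the end of the 28-day SAE period

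*Combined protocol and SAP*

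**What the plan says.** Section 5.3.1 makes AE reporting mandatory from consent "until the last visit of the treatment phase, 26 to 32 days after surgery". Other sections place the end of the treatment phase and the post-surgery visit as follows.

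- **4.5.4:** "Treatment phase ends on the day of surgery (Day 15 +/-1").
- **4.5.6:** the End of Study visit "occurs on treatment day 32 +/- 8, which represents a time point situated approximately at 2 to 3 weeks after surgery". Appendix A gives the same Day 32 +/- 8, calls it the End of Treatment visit and puts it under the follow-up phase.
- **4.5:** the follow-up phase is "Study Days 25 to 40", for both groups.
- **3.1.1:** "The End of Study visit will occur approximately 2 to 3 weeks after surgery".
- **3.2:** "The end of treatment visit will occur 32 (+/- 8 days) after surgery", and then, barring early stopping or delays, "this would result in 24-40 days on trial".
- **5.4.2.4:** SAEs are reportable from the first dose "through 28 calendar days after the last administration of the Pfizer Product". SAEs suspected to be related to palbociclib stay reportable after that.

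After the Day 32 +/- 8 column, Appendix A lists only the 1-year and 5-year follow-up. It marks a telephone contact in the Day 32 +/- 8 column, but gives it no date of its own and no AE content.

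**The concern.** Section 5.3.1 is the operative rule for when AE collection stops. It names a last visit of a phase that 4.5.4 closes at surgery, and its day count does not match the schedule. A coordinator who stops at the scheduled visit and one who applies the days in 5.3.1 would collect AEs for different lengths of time.

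Toxicity is the secondary endpoint and is summarised descriptively, with 12 treated patients at two centres. Unequal collection periods would feed directly into the AE counts.

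The scheduled visit also usually comes before the 28-day SAE period ends. In the days between, events would reach the investigator only if patients volunteer them or staff happen to see them. Section 5.3.2 says that patients will also be asked about AEs, but no contact for asking is fixed in that interval.

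**Working it through.** **Inputs.** Last dose: Day 12 (3.1.1). Surgery day s: 14, 15 or 16 (3.1.1, 4.5.5). Visit day v: 32 +/- 8, so Day 24 to 40, 17 permitted days (4.5.6, Appendix A). Reporting end: s + 26 to s + 32 (5.3.1). SAE period: 28 days after the last dose (5.4.2.4).

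**The plan's own figures.**
- About 2 to 3 weeks after surgery: 32 - 15 = 17 days. This reproduces.
- 24 to 40 days on trial (3.2): 32 - 8 = 24 and 32 + 8 = 40, counted from Day 1. This reproduces.
- 26 to 32 days after surgery (5.3.1): v - s runs from 24 - 16 = 8 to 40 - 14 = 26. Of the 3 x 17 = 51 combinations of surgery and visit day, only one (surgery Day 14, visit Day 40) reaches 26. This does not reproduce.

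**5.3.1 against the schedule.**

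| Surgery day | 5.3.1 in study days | Days after last dose | Shared with Day 24 to 40 |
|---|---|---|---|
| 14 | 40 to 46 | 28 to 34 | Day 40 only |
| 15 | 41 to 47 | 29 to 35 | none |
| 16 | 42 to 48 | 30 to 36 | none |

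The Day 25 to 40 window in 4.5 gives the same result.

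**Difference in collection time, surgery on Day 15.** With a Day 32 visit, reporting stops 41 - 32 = 9 to 47 - 32 = 15 days earlier than under 5.3.1. Over the whole visit window the difference is 41 - 40 = 1 to 47 - 24 = 23 days.

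**Literal reading of 3.2.** Counted from surgery, 32 +/- 8 days means 24 to 40 days after surgery, which does contain 26 to 32. In study days it is 14 + 24 = 38 to 16 + 40 = 56, nominally 15 + 32 = 47. That contradicts 3.2's own 24 to 40 days on trial, and also 3.1.1, 4.5, 4.5.6 and Appendix A.

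**SAE period.** 12 + 28 = Day 40. The scheduled visit is 24 - 12 = 12 to 40 - 12 = 28 days after the last dose. It precedes Day 40 on 16 of 17 permitted days (15 of 16 under 4.5), by 40 - 32 = 8 days at the nominal date and by up to 40 - 24 = 16.

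**Where a count from Day 1 fails.** Day 1 is defined as the first palbociclib day, so Day 32 has no meaning for Group B. If surgery is postponed 7 days for cytopenia (3.1.1), from Day 15 to Day 22, a fixed Day 24 to 40 falls only 24 - 22 = 2 to 40 - 22 = 18 days after it.

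**Window stated from surgery.** 32 - 15 = 17, so 17 +/- 8, or 9 to 25 days after surgery, keeps the present width.

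| Surgery day | Visit window | Permitted days on or after Day 40 |
|---|---|---|
| 14 | Day 23 to 39 | 0 of 17 |
| 15 | Day 24 to 40 | 1 of 17 |
| 16 | Day 25 to 41 | 2 of 17 |
| 22 | Day 31 to 47 | 8 of 17 |

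A later contact is therefore still needed in most cases.

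**The case against.** The strongest reply is that 5.3.1 plainly means the End of Treatment visit, which the schedule does contain, and simply carries a wrong day count. Sections 5.3.1 and 3.2 even agree as literally written. The first part stands: a reader might infer that 5.3.1 refers to a visit that exists nowhere, and the documents do not support that. The second does not rescue 5.3.1, because the literal 3.2 wording fails against its own days on trial and against the schedule.

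A reader might also infer that SAE reporting lapses after the clinic visit. It does not. Section 5.4.2.4 depends on no visit, and suspected-related SAEs remain reportable at any later time. Section 5.3.2 also requires observed and spontaneously reported events to be recorded. The weakness is in scheduled questioning, not in the duty to report.

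Nor is it right that no telephone contact is planned. Appendix A marks one, and it could fall as late as Day 40. Nothing requires that date, however, or an AE question.

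The impact is also limited. Toxicity is descriptive with no group comparison, safety is reviewed weekly (5.4.7), and the clinic visit includes a blood count. The nadirs cited in 3.4.2, under longer dosing, fall between Days 15 and 22. These points lower the weight of the problem, but they do not tell a site when to stop collecting.

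Finally, the visit itself could move to 26 to 32 days after surgery. That would cover 28 days post-dose with a blood count and no extra call. But it departs from the 2 to 3 weeks in 3.1.1 and 4.5.6 and delays the visit at which pathology and further treatment are discussed.

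**Conclusion.** The point holds as an inconsistency in an operative safety rule. For an on-schedule Group A patient with surgery on Day 15 or 16, no visit day meets both 5.3.1 and the schedule; with surgery on Day 14, only Day 40 does. At the nominal visit the two readings differ by 9 to 15 days of AE collection, and the visit comes 8 days before the SAE period ends.

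These figures assume all 12 doses are taken and surgery is on time. If palbociclib stops by Day 4, a Day 32 visit does reach 28 days after the last dose (32 - 28 = 4). The 28-day period does not apply to Group B.

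A reader might go on to infer that the feasibility criterion in 2.3 is compromised, because it counts patients whose follow-up kept to the protocol. The documents do not show this. Appendix A is the natural window for that count, and nothing indicates that any patient's classification or the 50% threshold would change. Sample size and inference are unaffected. The change should be made, but the trial's primary conclusions do not depend on it.

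**What to change.** 1. **Visit window.** In 3.2, correct the visit to Day 32 +/- 8 as in Appendix A. State the window from surgery, about 17 +/- 8 days after it, so that it also serves Group B and postponed surgery. Keep 3.1.1, 4.5, 4.5.6 and Appendix A consistent with it. The full window of 9 to 25 days is wider than 2 to 3 weeks, as the present one is, so those phrases should be marked as the target.
2. **End of AE reporting.** In 5.3.1, replace the present end point with at least 28 days after the last palbociclib dose for Group A, and with the post-surgery visit for Group B. When the Group A clinic visit is earlier, place the telephone contact already listed in Appendix A at or after 28 days post-dose, with AE questioning. That is Day 40 or later if all 12 doses are taken, and 28 days after the actual last dose if treatment stops early.

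**Cost.** Up to about 12 dated calls, plus one for any patient who took palbociclib and was then substituted, and a wording amendment that needs IRB approval (8.6). A call gives no blood count, so a cytopenia arising after the clinic visit would be found only through symptoms or local tests.
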